6. Be sure to submit **data collection instruments** for review with your e-IRB Application (e.g., measures, questionnaires, interview questions, observational tool, etc.).

The study member will screen for potential subjects using the UCIMC surgical schedule. If a subject is deemed ineligible based on the inclusion and exclusion criteria after reviewing the medical history, his/her record will be discarded. No records will be retained from ineligible subjects. After discussing with the patient's surgeon, study team member will initiate the informed consent process by approaching each eligible subject to explain the study and what it entails. The Lead Researcher will address all questions and concerns from the subject before asking the subject to sign the research consent form.

The GE anesthesia machines currently owned by the operating room will be used to serve as the comparator to the Flow-i machine. The high volume anesthesia machines do not use a low volume system. Subjects will be randomized by recruitment day. On a given recruitment day, all consented subjects will receive anesthesia from one of two groups:

- (1) MAQUET FLOW-i device
- (2) GE anesthetic device

Time points for both groups include:

T₀: Time of intubation, when volatile anesthetic are typically first delivered to the patient. We will use 15L/min fresh gas flow, while dictating tidal volumes of 6-8 mL/kg ideal body weight and a PEEP of 6 centimeters of water (cm H₂O) in accordance with current best practices.

T₁: Time of incision, which typically represents the time of reaching steady state conditions of volatile anesthetic delivery. We will reduce fresh gas flow to 2 L/min in accordance with local practice and weigh the vaporizer at this point, allowing us to measure comparative anesthetic consumption during this wash-in time period (T₀-T₁).

T₂: Time of anesthetic weaning, typically the time when preparing for patient emergence begins by discontinuing the delivery of volatile anesthetics to the patient. The vaporizer will be re-weighed at this point, allowing us to measure comparative anesthetic consumption at steady state maintenance of anesthetic depth (T₁-T₂)

Logically, we will also be able to use T₀-T₂ in order to understand total comparative anesthetic consumption.

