Aside from the randomization to either Group 1 or Group 2, there will be no changes in the surgical or anesthetic procedure, including the medication or treatments given to the subjects as determined by the treating physician. All subjects will receive general anesthesia in accordance to local practice.

For this study, the vaporizer(s) will be weighed on a tared scale before research procedures commence, after induction, and when the gas is shut off during weaning of anesthesia in preparation for extubation to calculate the amount consumed during this time (grams/minute). In addition, the following variables will be recorded:

- Subject weight (kg)
- Tidal Volume (TV)
- Respiratory Rate (RR)

- Positive end-expiratory pressure (PEEP)
- Fresh Gas Flow
- Volume % gas
- End Tidal (%)
- Time of extubation
- Time when Aldrete score > 8

This is not a physician-blinded study being that the physical characteristics of the standard delivery units are distinguishable from the MAQUET FLOW-i machine.

All MAC concentrations are standard of care: After the surgical procedure, patient will be assessed for time to reach Aldrete score greater than 8, level of pain and time to extubation. Their medical records will be reviewed to determine need for times and adverse events. Patients will not be contacted for study-related follow-up after they are discharged from recovery.

No photographs or audio/video recording will be collected for this study.

Subject's Privacy:

The study team member will screen for potential subjects using the UCIMC surgical schedule. If a subject is deemed ineligible based on the inclusion and exclusion criteria after reviewing the medical history, his/her record will be discarded. No records will be retained from ineligible subjects.

Study team member will approach each eligible patient to explain the study and what it entails. The study team member will address all questions and concerns from the subjects before asking the patient to sign the research consent form.

B. Statistical Considerations

1. **Statistical Analysis Plan:** Describe the statistical method(s) for the stated specific aims and hypotheses described in Section 1. *Note: Required for scientific review.*
2. **Explain how the overall target sample size was determined** (Provide power / sample size justification for the study).

If a statistical analysis plan is not appropriate for your study design, please describe a plan for assessing your study results.

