The primary purpose of this study is to evaluate the Maquet anesthesia workstation in regards to savings of volatile agent compared to conventional machines. As the Maquet workstation is more expensive than conventional machines, there must be a substantial cost-savings in terms of volatile agent to offset the additional up-front cost. The typical service life of an anesthesia workstation is around 5 years. For powering this study we decided that to be cost-effective the Maquet machines must save enough volatile agent in 1.5 years to offset the cost-difference, leaving the remaining service lifetime as profit over conventional machines.

Since volatile agent use is not recorded on a per-case basis, nor is it possible to determine from the anesthesia intra-op record, we also needed to estimate the approximate volatile use per case. Volatile use increases with length of case, fresh gas flow rate, and vaporizer percent-saturation setting. From pharmacy purchase records, we know that the average monthly Sevoflurane purchase over the past two years at UCI is $\$11,700 \pm \$6,200$. Averaged out over approximately 20 OR locations using Sevoflurane daily and about 30.5 days in a month, this gives us $\$19.2 \pm$

10.2 per OR per day cost. Finally, assuming 40 cases per day in the main OR spread over those 20 rooms gives us two cases per day on average per room, or $\$9.6 \pm 5.0$.

The cost difference in the Maquet machines is approximately \$50,000 over conventional machines, meaning the total Sevoflurane reduction must amount to \$50,000 over 1.5 years. With \$11,700 per month average over 1.5 years totaling \$210,000, a \$50,000 reduction represents about a 25% reduction in total use.

So, assuming we will have two groups (Maquet and conventional) for which we will measure Sevoflurane use during cases, the Maquet machine must use 25% less Sevoflurane to be cost-effective. With a per-case cost of $\$9.6 \pm 5.0$ for the conventional group, we must have sufficient power to differentiate whether the Maquet group has a cost of $\$7.2 \pm 5.0$ per case (assuming equal case variance for this group).

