With a power of 0.8 (20% type II risk), a significance level of 0.05 (type I risk of 5%), and using a one-sided t-test to compare groups, we require two groups of 55 patients (n=110 total) in each group – Group 1: Maquet Anesthesia Machine, Group 2: GE Anesthesia Machine – to detect a 25% change in cost. An additional 11 subjects (10% attrition rate) will be included to the target sample size to account for unforeseen circumstances leading to an exclusion i.e. mechanical failure, incomplete data, different anesthetic device etc.

SECTION 4: SUBJECTS (PERSONS/CHARTS/RECORDS/SPECIMENS)

A. Number of Subjects (Charts/Records/Biospecimens)

1. Indicate the **maximum number of subjects to be recruited/consented** on this UCI protocol. This is the number of potential subjects you may need to recruit to obtain your target sample size. This number should include projected **screen failures and early withdrawals**. *Note: The IRB considers individuals who sign the consent form to be "enrolled" in the research.*
2. For **Mail/Internet surveys** include the number of people directly solicited.
3. If the study involves use of **existing charts, records, biospecimens**, specify the maximum number that will be reviewed/tested to compile the data or the sample population necessary to address the research question.

1. The maximal sample size is 128 subjects. The target sample size at UCI is 110 subjects. 55 patients for Group 1 (Maquet), 55 patients for Group 2 (GE machine)

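### The only comparison named is an unadjusted t-test; adjusting for recorded body weight would be a free, probably modest, gain in precision

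*Combined protocol and SAP*

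**What the plan says.** Section 3.B (Statistical Considerations) contains no separate description of the primary analysis. The one method it names is in the sample-size paragraph: "using a one-sided t-test to compare groups". That paragraph goes on to say "we require two groups of 55 patients (n=110 total) in each group", for 80% power at the 5% level. No regression model or covariate appears anywhere in the supplied text.

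In Section 3.A, the list of variables to be recorded opens with "Subject weight (kg". No use for it is stated, and neither is the time at which it is measured. The same section scales ventilation to body size, "dictating tidal volumes of 6-8 mL/kg ideal body weight", and allocates machines by recruitment day, so that all subjects consented on a day receive the same machine.

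Three other statements bear on the point:

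- Section 1 defines the primary variable per minute of anaesthesia.
- Section 3.B names the drivers of volatile use as case duration, fresh gas flow and vaporizer setting. Weight is not among them.
- Section 4.B excludes subjects with a BMI above 30.

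**The concern.** A baseline variable that predicts the outcome can be put into the model to remove the variance it explains. The standard error of the difference then shrinks with no extra patients. Adjustment also corrects for any chance difference between arms in that variable, which an unadjusted t-test leaves in the estimate.

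Weight is the natural candidate here. Of the variables in the Section 3.A list, it is the only patient characteristic that the allocated machine cannot change. The plan collects it and then leaves it out of the only comparison described.

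What is at stake is the width of the interval for the saving, and a power that, on the plan's own inputs, is only just above its 0.80 target.

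**Working it through.** **Inputs from Section 3.B:** conventional mean $9.6 per case; Maquet mean $7.2 per case; common SD $5.0; one-sided alpha 0.05; power 0.80; 55 per arm.

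**Input not in the documents:** the correlation r between weight and the outcome. It is assumed, over the range 0 to 0.4.

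**Step 1: reproduce the plan's figure.** The difference is 9.6 − 7.2 = 2.4, so the standardised difference is 2.4 / 5.0 = 0.48. The noncentrality parameter is 2.4 / (5.0 × √(2/n)).

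- n = 54: noncentrality 2.494, 106 df, power 0.798.
- n = 55: noncentrality 2.517, 108 df, critical value 1.659, power 0.804.

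The smallest n reaching 0.80 is 55, as stated. The two-sided version would need 70, so the figure is indeed that of the one-sided t-test without covariates.

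**Step 2: add weight.** Residual SD = 5.0 × √(1 − r²), with 107 df instead of 108. Power again comes from the noncentral t distribution at 55 per arm.

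| r | Residual SD | Reduction in standard error | Power at 55 per arm | n per arm for 0.80 |
|---|---|---|---|---|
| unadjusted | 5.000 | – | 0.8041 | 55 |
| 0 | 5.000 | none | 0.8041 | 55 |
| 0.1 | 4.975 | 0.5% | 0.808 | 54 |
| 0.2 | 4.899 | 2.0% | 0.818 | 53 |
| 0.3 | 4.770 | 4.6% | 0.836 | 50 |
| 0.4 | 4.583 | 8.3% | 0.861 | 46 |

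At r = 0 the change is from 0.80413 to 0.80409, a loss of 0.00004.

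**Step 3: what these figures do not cover.**

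- *Scale.* The $5.0 comes from the spread of monthly purchases: 6,200 / (20 × 30.5) = 10.16 per room per day, and half of that is 5.08 per case, which the plan writes as 5.0. It is neither a between-patient SD nor the SD of grams per minute. The table shows how a given r changes power on the plan's own inputs, and no more than that.
- *Allocation by day.* The table treats the 110 patients as independent. As an example with assumed values, 3 patients per day and an intraclass correlation of 0.05 give a design effect of 1 + 2 × 0.05 = 1.1, or 55 / 1.1 = 50 effective patients per arm. By the normal approximation, power is then 0.775, against 0.808 with no clustering. That loss of about 3 points is as large as the gain at r = 0.3.

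**The case against.** The strongest reply is that nothing in the documents shows weight to matter. It is not among the drivers named in Section 3.B. The outcome is already per minute, Section 3.A specifies the same fresh gas flows for both arms, and the BMI limit narrows the range of weight. A correlation of 0.1 or 0.2 is at least as plausible as 0.3 or 0.4, and the gain is then 0.3 or 1.4 percentage points. An unadjusted comparison is also valid as far as weight is concerned. All of this stands and limits the priority of the point. It does not argue against adjusting, because the cost at r = 0 is negligible and no other part of the plan provides the adjustment.

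Several stronger readings are tempting, and the documents do not support them:

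- *Weight is a pre-randomisation variable, so adjustment cannot bias the comparison.* The day is randomised, Section 5.B has consent finalised on the day of surgery, and no time is given for weighing. A day's allocation may therefore precede enrolment. What can be said is that weight is a baseline value the machine does not affect, and that adjusting for it adds no bias of practical concern. If the day's machine is known at consent, adjusting for weight does not repair selection.
- *The tidal-volume rule shows that recorded weight drives consumption.* That rule uses ideal body weight. The recorded variable is not described as ideal weight, and height is not in the list.
- *Whole-day allocation makes imbalance in weight more likely.* This holds only if weight clusters by day, for example through the surgical list. No section shows that it does.
- *The t-test is the declared final analysis.* It is stated only as the basis for the sample size. Taking it as the primary analysis is a reasonable inference, because nothing else is given.

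**Conclusion.** The point holds as a free improvement of low priority. The plan records a usable baseline covariate and leaves it out of the only comparison it describes. The 55 per arm is correct for the test and inputs stated, and a reader should not infer that the sample size is wrong or that the t-test is invalid for want of this covariate.

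The size of the benefit is unknown because r is not documented. On the plan's inputs it runs from practically nothing at r = 0 to 5.7 percentage points of power at r = 0.4, and it is about 3 points or less for r up to 0.3. These values assume independent patients and the $5.0 per-case SD, so they must not be quoted as the power of the grams-per-minute analysis. Correction of a chance imbalance in weight is a further benefit, of a size that cannot be stated. Adjusting for weight does not deal with randomisation by day, which needs its own provision in the same model.

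**What to change.** Before outcome data are examined, add to Section 3.B a primary analysis model: consumption in grams per minute regressed on arm and baseline body weight (continuous), with errors that account for randomisation by day. State that the weight used is one recorded before anaesthesia. Keep the unadjusted comparison as a sensitivity analysis.

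State also that fresh gas flow, volume % and end-tidal % are not covariates in this model. They are measured under the allocated machine, and adjusting for them could remove part of the effect under study.

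The cost is a few lines of text and one degree of freedom for the covariate. No new data and no change to the sample size are needed on this account. Fixing the covariate in advance avoids any suggestion that it was chosen after the results were seen.

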2. Provide the **relevant background information** on the aims/hypotheses (or research question) to be tested and the procedures/products/techniques under investigation.
3. Include a description of the **primary outcome variable(s), secondary outcome variables, and predictors** and/or comparison groups as appropriate for the stated study objectives.
4. Include a critical evaluation of **existing knowledge**, and specifically identify the information gaps that the project intends to address.
5. Describe **previous research** with animals and/or humans that provides a basis for the proposed research. **Include references/citations**, as applicable.

This section should not exceed 4 pages.

The purpose of this study is to test whether or not the use of a low volume ventilator in an anesthesia machine reduces anesthetic costs significantly as compared to other high volume machines. The study will compare the FLOW-i anesthesia machine to a GE anesthesia machine

during routine elective general surgery in patients with ASA ratings of 1-2 under general anesthesia receiving standard care.

General anesthesia based on the administration of inhaled anesthetics is common practice. The clinical use of sevoflurane is standard of care in the operating room. There are today a variety of anesthetic devices introducing the gas in somewhat different manners. The technical solution has an impact on entire gas consumption. Techniques providing safe and effective anesthesia but with a minimum of waste is sought in order to decrease direct drug related costs.

1. **Primary study variable:** amount of gas vaporized anesthetic per minute anesthesia.
2. **Secondary study variables:**
 - a. Time to reach Aldrete > 8
 - b. Time to extubation from weaning
 - c. **Maquet firmware-based volatile anesthetic consumption data**

Sevoflurane an inhaled halogenated anesthetic has physiochemical properties promoting its use in low flow anesthesia.

Low blood gas solubility promotes in theory the use of the third generation inhaled anesthetics for use during general anesthesia with low fresh gas flow. The benefits of low blood and tissue solubility during low and minimal flow are not yet studied.

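### Time to Aldrete > 8 (secondary) has no stated time origin, and no masking of its scorer is planned, although the reason given for not blinding physicians does not require an unmasked postoperative scorer

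*Combined protocol and SAP*

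**What the plan says.** Section 1 lists three secondary variables. The first is "Time to reach Aldrete > 8", with no starting point. The second is "Time to extubation from weaning", which has one.

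The procedures narrative in Section 3 (before 3.B) defines T0, T1 and T2 for weighing the vaporizer. T2 is the "Time of anesthetic weaning, typically the time when preparing for patient emergence begins by discontinuing the delivery of volatile anesthetics to the patient". None of the three is tied to Aldrete. The list of recorded variables contains "Time when Aldrete score > 8", which is a clock time and not a duration. The same narrative says that once surgery is over the "patient will be assessed for time to reach Aldrete score greater than 8, level of pain and time to extubation". It gives no scorer, place or scoring interval. Recovery appears only as the end of follow-up: "Patients will not be contacted for study-related follow-up after they are discharged from recovery".

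The only statement on blinding is "This is not a physician-blinded study being that the physical characteristics of the standard delivery units are distinguishable from the MAQUET FLOW-i machine". On allocation: "Subjects will be randomized by recruitment day", so every subject on a given day gets the same machine.

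**The concern.** Two things are left open for this outcome.

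**The origin.** A duration needs a start. Weaning, extubation, end of surgery and arrival in recovery all fit the text, and each gives a different variable. If none is fixed in advance, the choice can be made after the data are seen. Some choices also omit part of the interval after the vaporizer is turned off, in which the machines could differ.

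**The scorer.** Aldrete is partly a matter of judgment, and the outcome is the time at which a threshold is first crossed, so a small lean in scoring moves the result. The visible difference between machines makes it hard to blind those who work at them. It is not a reason for a postoperative scorer to be told which one was used. Because one machine serves a whole recruitment day, anyone who knows that day's assignment knows the arm of every subject.

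Aldrete and extubation times are the only patient-recovery outcomes among the listed secondary variables. Any statement that lower agent use did not slow recovery would rest on them.

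**Working it through.** **1. The plan's own figure.** Section 3.B sizes the primary comparison only: $9.6 against $7.2 per case (difference 2.4), SD 5.0, one-sided 5%, power 0.80.

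- Normal approximation: n = 2 × (1.645 + 0.842)² × (5.0/2.4)² ≈ 53.7, so 54 per group.
- Exact one-sided t-test: 54.4, so 55 per group, with power 0.804 at 55.

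The stated 55 per group reproduces. No difference, SD or power is given for Aldrete, so the rest is either a reading of the text or an illustration.

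**2. The two recovery outcomes side by side.**

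| Item | Time to extubation | Time to Aldrete > 8 |
|---|---|---|
| Origin | weaning | not stated |
| End | clock time recorded | clock time recorded |
| Scorer | not stated | not stated |
| Place and scoring interval | place not stated; single event | neither stated |
| Masking | physicians not blinded | scorer not mentioned |

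The form's instructions in Section 3 ask for the blinding scheme, precise endpoint definitions, the setting of each procedure and the spacing of repeated ones. The answers supply none of these for Aldrete.

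**3. Illustration of scale.** Assumptions not in the documents: two-sided 5%, 55 per arm, individual-level t-test. The detectable standardized difference at 80% power is d = 0.539.

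*Differential scoring.* With no true difference and a shift of b SD between arms, the noncentrality is b × √(55/2) = 5.244b.

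| b (SD) | False-positive rate |
|---|---|
| 0 | 0.05 |
| 0.1 | 0.08 |
| 0.2 | 0.18 |
| 0.3 | 0.35 |

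*Non-differential timing noise.* If the noise SD is r times the true SD, d becomes 0.539/√(1 + r²).

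| r | d | Power |
|---|---|---|
| 0 | 0.539 | 0.80 |
| 0.25 | 0.523 | 0.78 |
| 0.5 | 0.482 | 0.71 |
| 1.0 | 0.381 | 0.51 |

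These tables show sensitivity. They do not estimate what happens in this trial.

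**4. Why a T2 origin alone is not enough.** Suppose a patient is first scored 15 min after T2 (assumed) and is already above 8. Writing down 15 min records when someone first looked, which may be largely transfer time. What is known is that the threshold was reached at or before 15 min. That observation is left-censored. For other patients the crossing lies between the last score of 8 or less and the first score above 8, which is interval-censored.

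**The case against.** The case against has real force.

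- **Silence is not an open-label rule.** The blinding sentence concerns physicians and does not mention the Aldrete scorer. A reader might infer that the plan lets anyone score, or that it deliberately leaves scoring open. The text does not say so. The Section 2 answers on team roles and the opening of Section 3 are not in the available text, and medical records are to be reviewed for times, so routine charting may be the source.
- **Place is unknown.** A reader might infer that Aldrete is scored in recovery, away from the machine, and that transfer delay is therefore already in the measure. The text places scoring only after surgery, in a sentence that also covers extubation.
- **The origin can be repaired.** The primary outcome is in grams per minute, so the T2 time must be captured. A T2 origin can be set without new data, and nothing proposes counting from arrival in recovery.
- **Loss of effect is easy to overstate.** A reader might infer that counting from arrival would make a true difference largely disappear. If 30–60% of patients were already above 8 on arrival (assumed) and arrival time did not depend on the machine, flooring at zero would keep roughly the share not yet above 8: 1 − 0.6 = 40% to 1 − 0.3 = 70% of a small mean difference.
- **The stakes are limited.** This is an unpowered secondary outcome, and no hypothesis or margin on recovery is stated. Data go to the manufacturer de-identified, and no route from that sharing to the scorer is described.

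All of this stands as a limit on the claim. It does not supply an origin, and it gives no reason for the scorer to know the machine.

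**Conclusion.** The point holds in a limited form. In the available text, time to Aldrete > 8 has no origin and no masking of its scorer is planned. Visibly different machines do not by themselves require an unmasked postoperative scorer, and day-level allocation makes the arm easy to learn.

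The missing origin and interval alone would be a matter of detail. What makes this worth changing is that masking the scorer reduces possible bias at very little cost, and it cannot be added once scoring is done.

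The place of scoring, the current scorer and the size of any bias cannot be determined from the documents. The illustrative rates rest on assumed shifts and on treating patients as independent. The primary outcome, a weight, is untouched.

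**What to change.** 1. **Scorer.** Have Aldrete and pain scored by existing postoperative clinical staff who are not told which machine was used. Study staff who know that day's allocation do not score. Keep the statement that the operating-room team is unblinded.
2. **Unmasking.** Record whether the scorer learned the machine. This is likelier than under individual randomization, because learning one patient's machine reveals the whole day's.
3. **Origin and interval.** Define the outcome as minutes from T2, matching extubation, with the same scoring interval in both groups. State where scoring takes place.
4. **First score.** Record its clock time. Treat patients already above 8 at that score as having reached the threshold at or before it, and analyse the times as left- or interval-censored. Report time from T2 to first score by group, so that any difference in transfer is visible.

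The cost is protocol wording, a hand-over instruction, one extra recorded time and a slightly less simple analysis. It relies on postoperative staff being available to score, which the documents do not confirm. The main downside is imperfect masking, which item 2 makes visible. If scoring has already taken place, items 1 and 2 can no longer be applied. The T2 origin can still be adopted, and item 4 can be followed where the charts hold the score times.

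### The SD of 5.0 dollars per case behind 55 per arm is a rescaled spread of monthly hospital purchases, not a between-patient SD, so the stated 80% power is unsupported

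*Combined protocol and SAP*

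**What the plan says.** Section 3.B is open about its difficulty: "Since volatile agent use is not recorded on a per-case basis", so "we also needed to estimate the approximate volatile use per case". The chain has four steps.

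- **Start:** "From pharmacy purchase records, we know that the average monthly Sevoflurane purchase over the past two years at UCI is" 11,700 ± 6,200 dollars. The ± is not labelled as an SD or a standard error.
- **Per room per day:** divided by about 20 rooms and 30.5 days, giving 19.2 ± 10.2 dollars.
- **Per case:** divided by two cases per room per day, giving 9.6 ± 5.0 dollars.
- **Comparison:** 9.6 ± 5.0 (conventional) against 7.2 ± 5.0 (Maquet), "assuming equal case variance for this group".

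The sample size follows: "With a power of 0.8 (20% type II risk), a significance level of 0.05", one-sided t-test, 55 per group.

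The primary variable in Section 1 is on another scale, "amount of gas vaporized anesthetic per minute anesthesia". The procedures text before Section 3.B has the vaporizer weighed to obtain grams per minute. Section 4.A, item 9, asks for the source of the assumed variability. The answer refers back to Section 3.B.

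**The concern.** A two-sample t-test on patients needs the SD between patients within an arm. The plan's ± describes hospital purchases from month to month, which reflect ordering, stock and caseload. Dividing the mean by the number of cases gives a fair mean cost per case. Dividing the ± by the same number does not give the spread between cases.

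The 55 per arm and the 80% power both rest on this one figure. If the true spread is larger, the trial could miss a 25% saving, the plan's own threshold for cost-effectiveness, more often than one time in five. If it is smaller, the trial has more power than stated.

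**Working it through.** **1. The plan's SD.** Inputs are from Section 3.B.

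- Cases per month: 20 × 30.5 × 2 = 1,220
- Mean: 11,700/1,220 = 9.59 dollars
- Spread: 6,200/1,220 = 5.08 dollars, given as 5.0
- Monthly CV: 6,200/11,700 = 0.530. Per-case CV used: 5.0/9.6 = 0.521

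Apart from rounding, the patient CV is the purchasing CV.

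**2. The plan's sample size.** Difference 9.6 − 7.2 = 2.4; effect size 2.4/5.0 = 0.48; one-sided 0.05; noncentral t with noncentrality 0.48 × √(n/2).

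- n = 54 per arm: power 0.798
- n = 55 per arm: power 0.804

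So 55 is reproduced. With the unrounded 5.08, power at 55 is 0.793 and 57 per arm are needed, a trivial difference.

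**3. Could the monthly spread reflect patient spread?** As an illustration, treat a monthly total as the sum of 1,220 independent cases.

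- A per-case SD of 5 moves the monthly total by 5 × √1,220 = 175 dollars, not 6,200.
- A monthly SD of 6,200 would need a per-case SD of 6,200/√1,220 = 178 dollars, or 177.5/9.59 = 18.5 times the mean.
- If 6,200 is instead a standard error over 24 months, the monthly SD is 6,200 × √24 = 30,374 and the gap widens.

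The 178 dollars is not a plausible SD. It shows that the monthly figure is dominated by something other than variation between cases.

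**4. What 55 per arm delivers.** A 25% relative reduction carries over to grams per minute if case lengths are similar in the two arms. Effect size is 0.25/CV, where CV is the SD divided by the GE mean. For equal CVs the Maquet SD is 0.75 of the GE SD, so the average variance is CV² × (1 + 0.75²)/2. All CVs are assumed, and patients are taken as independent.

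| GE-arm CV | Power, equal SDs | Power, equal CVs |
|---|---|---|
| 30% | 0.997 | >0.999 |
| 40% | 0.95 | 0.98 |
| 52% | 0.81 | 0.88 |
| 60% | 0.70 | 0.79 |
| 70% | 0.59 | 0.68 |
| 80% | 0.49 | 0.58 |

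The largest CV that gives 80% power is 52.4% with equal SDs and 59.3% with equal CVs. For 90% power the limits are 44.5% and 50.4%.

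**5. Assignment by day.** Machines are randomized by recruitment day: "On a given recruitment day, all consented subjects will receive anesthesia from one of two groups". With an assumed 3 patients per day, the design effect is 1 + (3 − 1) × ICC. At CV 52% with equal SDs, power is:

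| Assumed ICC | Design effect | Power | Power, df from about 18 days per arm |
|---|---|---|---|
| 0 | 1.00 | 0.81 | – |
| 0.05 | 1.10 | 0.77 | 0.76 |
| 0.10 | 1.20 | 0.74 | 0.73 |
| 0.20 | 1.40 | 0.68 | 0.67 |

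**The case against.** The plan hides nothing: it says case-level use is unavailable, shows each division and marks equal variance as an assumption. That counts in its favour, but nowhere does it say that 5.0 itself is an assumption about spread between patients.

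The true CV may well be below 52%. Grams per minute divides out duration, fresh gas flow is set in the procedures text, and Section 4.B restricts eligibility. This stands, and it is why the point is not that the trial is too small.

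A null result is better read from the confidence interval and the observed SD than from planned power. That also stands. The consequence is therefore mainly at the design stage, although a reader who sees only the stated 80% could still lean on it. It does not make the 80% supported.

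Relabelling 5.0 does not supply the source that Section 4.A, item 9, asks for. True: the documents hold no case-level data to draw on. The change makes the status of the figure plain, and the trial's own vaporizer weights could later fill the gap.

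The day-level correlation is a separate matter and its inputs are assumed. It belongs here only as a condition on the power table.

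**Conclusion.** The concern holds. The ± 5.0 dollars is 6,200 divided by 1,220 and does not estimate between-patient SD, whether 6,200 is an SD or a standard error. The documents contain no SD for grams per minute. The 55 per arm follows correctly from SD 5.0, but the 80% power has no support.

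The size of any error is unknown. Over assumed CVs of 30% to 80%, power at 55 per arm runs from 0.997 to 0.49 with equal SDs. The plan's value of 52.1% sits almost on the 52.4% limit. These figures assume a 25% true reduction, a one-sided 0.05 t-test and independent patients. Nothing here shows that the trial is underpowered or biased. It should be fixed, and the fix is cheap.

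**What to change.** In Section 3.B:

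1. State that 5.0 dollars (CV about 52%) is a planning assumption and not a between-patient SD estimated from purchase records.
2. Restate the calculation for grams per minute with a 25% relative reduction.
3. Replace the flat 80% with power at 55 per arm over a range of CVs, using the equal-SD column above. Beside it, give the 52.4% limit (about 59% for the GE arm if CVs are equal). Say that the table assumes independent patients and that randomization by day would lower the figures if same-day patients are correlated.

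Optionally, report an arm-blind SD of grams per minute from the vaporizer weights, with its uncertainty. For independent, normally distributed values the 95% limits are 0.76 to 1.46 times the estimate from 20 cases and 0.80 to 1.34 times from 30. Same-day correlation would make these limits too narrow. State the divisor. If the 25% difference is real and the within-arm SD is 52% of the GE mean, the arm-blind SD is √(0.52² + 0.125²) = 53.5% of the GE mean, or 0.535/0.875 = 61% of the pooled mean.

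The cost is some wording and one small table. Patient numbers, test, decision rule and data collected do not change. The drawback is that the power statement may look less favourable than 80%.
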